9.1.1.3 Abnormal Laboratory Values

Only clinically significant laboratory abnormalities that require active management will be recorded as AEs or SAEs on the CRF (e.g., abnormalities that require study drug dose modification, discontinuation of study treatment, more frequent follow-up assessments, further diagnostic investigation, etc.).

If the clinically significant laboratory abnormality is a sign of a disease or syndrome (e.g., alkaline phosphatase and bilirubin 5 x the upper limit of normal associated with cholecystitis), only the diagnosis (e.g., cholecystitis) needs to be recorded on the Adverse Event CRF.

If the clinically significant laboratory abnormality is not a sign of a disease or syndrome, the abnormality itself should be recorded as an AE or SAE on the CRF. If the laboratory abnormality can be characterized by a precise clinical term, the clinical term should be recorded as the AE or SAE. For example, an elevated serum potassium level of 7 mEq/L should be recorded as “hyperkalemia”

Observations of the same clinically significant laboratory abnormality from visit to visit should not be repeatedly recorded as AEs or SAEs on the CRF, unless their severity, seriousness, or etiology changes.

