1.5 Risks Associated with NKTR-102

A majority of NKTR-102 related treatment-emergent adverse events (TEAEs) occurred in the system organ class (SOC) of GI disorders with diarrhea experienced most commonly by 85.5% of patients, followed closely by nausea (77.6%), fatigue (51.3%), and vomiting (48.7%). Other clinically significant NKTR-102-related TEAEs with an incidence rate > 10% included anorexia, dehydration, alopecia, electrolyte disturbances like hypokalemia and hypomagnesemia,

abdominal pain, anemia, and blurred vision, in decreasing order of frequency. Prolonged severe diarrhea with dehydration leading to pre-renal azotemia and subsequent acute renal insufficiency has been fatal in three patients in the ongoing Phase II studies in metastatic colorectal, ovarian, and breast cancers (one patient in each study). To date, early onset cholinergic diarrhea (as seen with irinotecan) has not been observed in any patient who received NKTR-102. Given the extended $t_{1/2}$ of SN38 derived from NKTR-102 (approximately 50 days), late onset diarrhea may occur and can be life-threatening if treatment is delayed. Early, proactive, and aggressive intervention with anti-diarrheal therapy, IV hydration, and maintenance of electrolyte balance is essential to prevent volume depletion, electrolyte imbalances, and the development of kidney failure.

Myelosuppression, especially neutropenia, can occur in patients receiving NKTR-102. Neutropenia in the setting of dehydration and unresolving GI toxicities may lead to the development of life-threatening or fatal sepsis. To date across all clinical studies, three patients have died within 30 days from last dose of NKTR-102 due to potentially drug-related neutropenic sepsis or complications of neutropenic sepsis, such as septic shock.

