7.2.3 Dose Reductions

NKTR-102 doses for an individual patient may be reduced 25 mg/m² based on conditions listed in the **Table 3** below. Only 2 dose reductions are permitted. Subjects should be discontinued from the study treatment if toxicity requires a dose reduction beyond the 2 dose reduction steps. Dose re-escalation for NKTR-102 is not permitted.

Table 3. Dose Modifications Based on Toxicities

Toxicity NCI CTCAE Grade	During a Cycle: Recommended Guidelines for Management and Supportive Care	Day 1 of New Cycle: Dose Modifications Based on Worst Toxicity in Prior Cycle
Thrombocytopenia / Anemia / Neutropenia / Febrile Neutropenia		
Grade 1 or Grade 2	-	Maintain dose level

Grade 3
	
Platelets: consider platelet transfusion if active bleeding.
 
ANC: consider growth factor support in accordance with local guidelines.
 
Hgb: erythropoietin-stimulating agents or transfusion as appropriate.
 
If present on a treatment day, hold therapy for a week or until toxicity resolves to Hgb \geq 8 g/dL or 80 g/L; ANC \geq 1.5×10^9/L; platelets \geq 75×10^9/L, with a maximum of 28 days.
	
↓ 1 dose level after 1st occurrence. ↓ 1 dose level after 2nd occurrence. Discontinue patient after 3rd occurrence.

Grade 4
	
Platelets: consider platelet transfusion if platelets < 20K or with active bleeding.
 
ANC: consider growth factor support in accordance with local guidelines.
 
Antibiotic (Fluoroquinolones) should be initiated even in the absence of fever or diarrhea.
 
Hgb: consider erythropoietin-stimulating agents or transfusion as appropriate.
 
If present on a treatment day, hold therapy for a week or until toxicity resolves to Hgb \geq 8 g/dL or 80 g/L; ANC \geq 1.5×10^9/L; platelets \geq 75×10^9/L, with a maximum of 28 days.
	
↓ 1 dose level after 1st occurrence. ↓ 1 dose level after 2nd occurrence. Discontinue patient after 3rd occurrence.

Febrile Neutropenia
	
Subjects should be hospitalized immediately for IV antibiotic therapy if they develop neutropenic fever or sepsis (e.g., growth factor support; antibiotics); consider hospital admission.
	
↓ 1 dose level after 1st occurrence. ↓ 1 dose level after 2nd occurrence. Discontinue patient after 3rd occurrence.

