9 SAFETY EVALUATION

9.1 Adverse Events

9.1.1 Definition

An adverse event or adverse experience (AE) is any untoward medical occurrence associated with the use of a drug in humans, whether or not considered drug related. Therefore, an AE can be ANY unfavorable and unintended sign (including an abnormal laboratory finding), symptom, or disease temporally associated with the use of a medicinal (investigational) product, whether or not considered related to the medicinal (investigational) product (attribution of ‘unrelated’, ‘unlikely’, ‘possible’, ‘probable’, or ‘definite’).

An AE is considered “unexpected” if it is not listed in the investigator brochure or is not listed at the specificity or severity that has been observed; or if an investigator brochure is not required or available, is not consistent with the risk information described in the general investigational plan in other study-related documents.

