9.1.3 Reporting Adverse Events

Table 7. Guidelines for Routine Adverse Event Reporting for Phase II Studies (Regardless of Expectedness)

Attribution	Grade 1	Grade 2	Grade 3	Grade 4
Unrelated			X	X
Unlikely			X	X
Possible	X	X	X	X
Probable	X	X	X	X
Definite	X	X	X	X

- Routine AEs occurring between the start date of intervention until 30 days after the last intervention or until the event has resolved, the study patient is lost to follow-up, the start of a new treatment, or until the study investigator assesses the event(s) as stable or irreversible, will be reported. New information will be reported after it is received.

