11.5 Safety Analysis

As per NCI CTCAE v 4.0, the term toxicity is defined as adverse events that are classified as either possibly, probably, or definitely related to study treatment. Non-hematologic toxicities will be evaluated via the ordinal CTC standard toxicity grading. Hematologic toxicity measures of thrombocytopenia, neutropenia, and leukopenia will be assessed using continuous variables as the outcome measures (primarily nadir) as well as categorization via CTC standard toxicity grading. Overall toxicity incidence as well as toxicity profiles by dose level, patient and tumor site will be explored and summarized. Frequency distributions, graphical techniques and other descriptive measures will form the basis of these analyses.

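### Unmanaged Grade 1-2 anemia has no assured route into the toxicity tables, because Section 9.1.1.3 keeps it off the AE page and Section 11.5 leaves hemoglobin out of its hematologic measures (minor)

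*Combined protocol and SAP*

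**What the plan says.** Three parts of the protocol decide whether a laboratory change is recorded.

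- **Section 9.1.1 (definition of an AE)** covers "ANY unfavorable and unintended sign (including an abnormal laboratory finding), symptom, or disease" and sets no management threshold.
- **Section 9.1.1.3 (abnormal laboratory values)** is narrower: "Only clinically significant laboratory abnormalities that require active management will be recorded as AEs or SAEs on the CRF". Its examples are "abnormalities that require study drug dose modification, discontinuation of study treatment, more frequent follow-up assessments, further diagnostic investigation, etc", so the list is open.
- **Table 7 (Section 9.1.3)** marks Grades 1 to 4 for possible, probable and definite attribution, and Grades 3 and 4 only for unrelated and unlikely. It makes no exception for laboratory findings.

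For analysis, Section 11.5 states that "the term toxicity is defined as adverse events that are classified as either possibly, probably, or definitely related to study treatment". It then adds a separate treatment for blood counts: "Hematologic toxicity measures of thrombocytopenia, neutropenia, and leukopenia will be assessed using continuous variables as the outcome measures", primarily the nadir, together with CTC grade. Hemoglobin is not on that list. Non-hematologic toxicities, which would include chemistry, are graded on the ordinal CTC scale with no data source named. Section 11.6 promises the number and severity of all AEs, and Section 11.1 a summary of all AEs regardless of attribution.

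On anemia itself, the first block of Table 3 is headed "Thrombocytopenia / Anemia / Neutropenia / Febrile Neutropenia". Its Grade 1 or 2 row lists no during-cycle action and keeps the dose level. Section 1.5 names anemia among the related events with incidence above 10%: "abdominal pain, anemia, and blurred vision, in decreasing order of frequency".

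**The concern.** Toxicity is a secondary objective (Section 3.2) and the outcome in the correlative UGT1A1 objective (Section 3.3). A low-grade laboratory change that needs no intervention is an AE under 9.1.1 and reportable under Table 7 if related, but it stays off the CRF under 9.1.1.3. Because 11.5 builds toxicity on related AEs, a change that was never recorded as an AE is not counted as toxicity.

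For platelets, neutrophils and leukocytes the nadir analysis makes up for this. For hemoglobin it does not, and the protocol gives no reason for the difference, even though Table 3 treats anemia alongside the other cytopenias. At stake is the completeness of the low-grade anemia rate and, to a lesser degree, of low-grade chemistry rates.

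**Working it through.** The protocol states no figure to reproduce here, so the check is to follow a patient through the text.

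**Step 1. Can hemoglobin fall with no action required?** Inclusion criterion 8 requires Hgb of at least 9 g/dL. Section 7.2.1 allows retreatment at 8.0 g/dL or above. A patient who enters at 9 and falls to 8 meets the retreatment criterion, so the protocol requires no delay on hemoglobin grounds. For Grade 1-2, Table 3 requires no reduction and lists no supportive measure.

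**Step 2. Which routes lead into the toxicity tables?**

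| Route | Source | Unmanaged Grade 1-2 anemia |
|---|---|---|
| AE page | 9.1.1.3 | Not recorded, because active management is a condition |
| Nadir and CTC grade | 11.5, hematologic measures | Not covered, because only three cytopenias are named |
| Ordinal CTC grade | 11.5, non-hematologic toxicities | Not covered, because anemia is hematologic |

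No route is assured.

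**Step 3. The same check for chemistry.** Drug-related Grade 2 present on a treatment day leads to a hold (Section 7.2.1 and Table 3). A hold plausibly counts as active management, so the event would be recorded. What may be missed is Grade 1, and Grade 2 that resolves within the cycle, if the ordinal grading in 11.5 is taken from the AE page.

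**Step 4. Are the values available?** Yes. Table 4 schedules hematology (its footnote includes HGB) and chemistry at screening, Cycle 1 Day 1, weekly in Cycle 1, Day 1 of each later cycle, and the 30-day follow-up. No section plans to grade hemoglobin or chemistry from them.

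**Step 5. Size.** With N = 38 (Section 4.2), the expected number of patients on the AE page is 38 x p x m, where p is the true Grade 1-2 anemia incidence and m is the share of those cases that receive active management. The documents give neither, so both are assumed across a range.

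| Assumed p | True patients (38 x p) | m = 0% | m = 10% | m = 50% | m = 100% |
|---|---|---|---|---|---|
| 30% | 11.4 | 0 | 1.1 | 5.7 | 11.4 |
| 50% | 19.0 | 0 | 1.9 | 9.5 | 19.0 |
| 70% | 26.6 | 0 | 2.7 | 13.3 | 26.6 |

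The count is low whenever m is below 100%. The table fixes the direction. It does not estimate the amount.

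**The case against.** The strongest reply is that Sections 9.1.1.1 to 9.1.1.4 are conventions for what goes on the CRF, and that Table 7 then applies to whatever has been recorded. Read in that order, the specific laboratory rule comes first and there is no flat contradiction. This is a fair reading, although the protocol does not state it. It turns the conflict into one of scope, but unmanaged low-grade anemia is still not recorded, and 11.5 still leaves it out.

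Second, active management is defined broadly. Section 7.2 treats delays as dose modifications, discretionary transfusion (Section 7.3.3) would qualify, and more frequent follow-up is among the listed examples. Many low-grade events will therefore be recorded. This stands, and it is why the loss is confined to unmanaged cases.

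Third, 11.5 names no data source, so nothing forbids grading from laboratory values. That is true, but nothing requires it either, and the listing of three cytopenias suggests that hemoglobin is not included.

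Three stronger readings are tempting, and the documents do not support them:

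- **Sizing the loss from neutropenia.** Section 1.3.2 gives at most 20% for all grades and 11% for Grade 3/4, which might suggest that up to 9 of 20 points are lost. But 11.5 already covers neutropenia, 20% is an upper bound, and an ANC below the retreatment limit on Day 1 can lead to a delay and so to recording. Nothing shows that hemoglobin or chemistry would lose the same share.
- **Citing hypokalemia as a lost event.** Table 3, under diarrhea of any grade, calls for correction of electrolyte abnormalities, and Sections 7.3.1 and 7.3.2 call for electrolyte replacement. Correction is active management.
- **Claiming a downward bias against the drug program's all-grade rates.** The recording rules behind those rates are not given, and no comparison with them is planned.

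**Conclusion.** The point holds, in a narrow form and as a minor one. Followed as written, the plan does not assure that unmanaged Grade 1-2 anemia is counted, and it may miss Grade 1 or transient Grade 2 chemistry changes. This rests on two assumptions: that sites apply 9.1.1.3 as worded, and that 11.5's named hematologic measures are the only ones graded outside the AE page.

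The amount is unknown. The share of low-grade cases that would be managed is not in the documents, and over the assumed ranges the loss runs from none to all such cases.

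Grade 3-4 cytopenias carry dose steps in Table 3 and so meet the recording rule. Grade 3+ events are also summarized separately under 11.6. The primary endpoint is not touched. A reader might infer that sites will in fact differ in which rule they follow. The wording allows this, but the documents do not show it.

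**What to change.** In Section 11.5:

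- Add hemoglobin, by nadir and worst CTCAE grade, to the hematologic measures.
- State that the worst CTCAE grade per patient for hematology and chemistry is derived from the laboratory values already collected, wherever CTCAE has criteria for the value.
- Name those tables as the source of laboratory toxicity rates, and note that AE-page counts leave out unmanaged laboratory changes.

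In Section 9, reconcile 9.1.1.3 with 9.1.1 and Table 7, for instance by saying whether 9.1.1.3 is an exception to Table 7 for laboratory findings.

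The cost is some programming and a few sentences of wording. No new visit, blood draw or treatment rule is needed. The downside is that reported low-grade rates will be higher than those taken from the AE page alone, which the report should explain.

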9.1.1.4 Preexisting Medical Conditions (Baseline Signs and Symptoms)

A preexisting medical condition should be recorded as an AE or SAE only if the frequency, severity, or character of the condition worsens during the study. When recording such events on an Adverse Event CRF, it is important to convey the concept that the preexisting condition has changed by including applicable descriptors (e.g., “more frequent headaches”).

9.1.2 Grading and Relationship to Drug

The descriptions and grading scales found in the CTEP Version 4 of the NCI Common Terminology Criteria for Adverse Events (CTCAE) will be utilized for AE reporting. CTEP Version 4 of the CTCAE is identified and located at: http://ctep.cancer.gov/protocolDevelopment/electronic_applications/ctc.htm. AEs not covered by specific terminology listed should be reported with common medical terminology, and documented according to the grading scales provided in the CTCAE Version 4.

The relationship of event to study drug will be documented by the Investigator as follows:

- **Unrelated:** The event is clearly related to other factors such as the patient's clinical state, other therapeutic interventions or concomitant drugs administered to the patient.
- **Unlikely:** The event is doubtfully related to investigational agent(s). The event was most likely related to other factors such as the patient's clinical state, other therapeutic interventions, or concomitant drugs.
- **Possible:** The event follows a reasonable temporal sequence from the time of drug administration, but could have been produced by other factors such as the patient's clinical state, other therapeutic interventions or concomitant drugs.
- **Probable:** The event follows a reasonable temporal sequence from the time of drug administration, and follows a known response pattern to the study drug. The event cannot be reasonably explained by other factors such as the patient's clinical state, therapeutic interventions or concomitant drugs.
- **Definite:** The event follows a reasonable temporal sequence from the time of drug administration, follows a known response pattern to the study drug, cannot be reasonably explained by other factors such as the patient's condition, therapeutic interventions or concomitant drugs; AND occurs immediately following study drug administration, improves upon stopping the drug, or reappears on re-exposure.

9.1.3 Reporting Adverse Events

Table 7. Guidelines for Routine Adverse Event Reporting for Phase II Studies (Regardless of Expectedness)

Attribution	Grade 1	Grade 2	Grade 3	Grade 4
Unrelated			X	X
Unlikely			X	X
Possible	X	X	X	X
Probable	X	X	X	X
Definite	X	X	X	X

- Routine AEs occurring between the start date of intervention until 30 days after the last intervention or until the event has resolved, the study patient is lost to follow-up, the start of a new treatment, or until the study investigator assesses the event(s) as stable or irreversible, will be reported. New information will be reported after it is received.

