Objectives	
Primary Objective:
 
 To evaluate the 18-week progression free survival (PFS) rate of relapsed SCLC patients treated with NKTR-102. 
Secondary Objectives:
 
 To evaluate the objective response rate. To evaluate the duration of response. To evaluate the overall survival. To evaluate the toxicity of NKTR-102 in this patient population. 
Correlative Objective:
 
 To explore the correlation between UGT1A1 polymorphisms and NKTR-102 toxicities.
Study Design	This is a single stage Phase II study of relapsed small cell lung cancer patients who have received only one prior systemic therapy regimen. There will be 2 patient cohorts: those progressing on first-line therapy < 3 months after completion of treatment (Group A: chemo resistant) and those progressing on first-line therapy ≥ 3 months after completion of treatment (Group B: chemo sensitive). Etirinotecan pegol will be administered at 145 mg/m ² IV once every 3 weeks. Cycles will be repeated every 21 days (± 3 days) until disease progression. Patients who develop metastases in the central nervous system (CNS) as the only site of disease progression could receive therapeutic whole brain radiation therapy (WBRT), or gamma knife radiosurgery and after completion of WBRT continue on NKTR-102. Imaging studies are scheduled to be obtained after every other 21-day cycle.
Target Accrual and Study Duration	This study will accrue a total of 38 patients over approximately 3 years (Group A; 20 patients, Group B; 18 patients). Patients will be on study for approximately 18 – 24 months.
Study Procedures	
Adverse Events: From time of Cycle 1 Day 1 until 30 days after receiving last dose of study drug.
 
Hematology: ≤ 14 days prior to initiation of study drug, Cycle 1 (Day 1 and weekly), and prior to treatment on Day 1 of subsequent cycles, 30-Day Follow-Up.
 
Chemistry: ≤ 14 days prior to initiation of study drug, Cycle 1 (Day 1 and weekly), prior to treatment on Day 1 of subsequent cycles, 30-Day Follow-Up.
 
Physical Examination (including vital signs, body weight, and height):

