7.12 Evaluations Performed at 30 Day Follow-Up

- Medical history (Updated from previous clinical visit)
- Physical examination, including vital signs and body weight
- ECOG performance status
- Adverse events evaluation
- Hematology (4 hour fasting) (i.e., complete blood count (CBC) with automated differentials or the physician discretion; WBC, RBC, HGB, HCT, platelet, MCV, MCH, MCHC, %neutrophils, absolute neutrophils, %lymphocytes, absolute lymphocytes, %monocytes, absolute monocytes, %eosinophils, absolute eosinophils, %basophils, absolute basophils, %Large Unspecified Cells (LUC), %lymphocyte total, absolute lymphocyte total, platelet confirmation, and differential confirmation)
- Chemistry (4 hour fasting) (i.e., complete metabolic panel (CMP): chloride, CO₂, potassium, sodium, BUN, glucose, calcium, creatinine, total protein, albumin, total bilirubin, alkaline phosphatase, AST, ALT, A/G ratio, BUN/creatinine ratio, osmol (Calc), anion gap)

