7.13 Survival Follow-up

- Patients will also be followed for survival every 3 months following the 30 day follow-up visit. Survival follow-up assessments may be collected via telephone.

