7.14 Schedule of Procedures and Observations

The schedule of procedures and observations for this study is summarized in **Table 4** below.

Table 4. Schedule of Procedures and Observations

Tests and Procedures	Screening (≤ 14 Days Prior to Initiation of Study Drug)	Cycle 1		Prior to treatment on Day 1 of Subsequent Cycles (± 3 days)	30 Day Follow- Up (± 7 days)	Survival Follow- Up
		Day 1	Weekly ¹ (± 2 days)			
Informed Consent	X					
Medical History	X ²	X ³	X ³	X ³	X ³	
Physical Exam, (including vital signs, body weight, height) ⁴	X	X	X	X	X	
ECOG Performance Status	X	X	X	X	X	
Adverse Event Evaluation	X	X ⁵	X	X	X	
Tumor Assessment	X ⁶			X ⁷		
CT Scan/MRI Brain	X ⁸					

Tests and Procedures	Screening (≤ 14 Days Prior to Initiation of Study Drug)	Cycle 1		Prior to treatment on Day 1 of Subsequent Cycles (± 3 days)	30 Day Follow- Up (± 7 days)	Survival Follow- Up
		Day 1	Weekly ¹ (± 2 days)			
Pregnancy Test (urine or serum)	X ⁹					
Coagulation (INR, PTT)	X					
Hematology (4 hour fasting) ¹⁰	X	X	X	X	X	
Chemistry (4 hour fasting) ¹¹	X	X	X	X	X	
Pharmacogenetic Blood Sample		X ¹²				
12-Lead ECG ¹³	X			X ¹⁴		
Survival Follow-Up						X ¹⁵

- 1 Patients will be evaluated weekly during Cycle 1 only. Complete physical examination is not mandatory but will be performed as needed at the discretion of the treating physician.
- 2 Full medical history.
- 3 Updated medical history from previous clinical visit.
- 4 Height collected at baseline only.
- 5 Reassess the patient for adverse events just prior to administration of the first dose of study drug on Day 1 Cycle 1. (Reassess adverse events on Day 1 of subsequent cycles and modify dose if necessary according to the dose modification **Table 3**, if clinically indicated, for Grade 2 or higher adverse events).
- 6 Imaging studies such as chest x-ray, CT scans, PET-CT, and MRIs can be performed ≤ 28 days prior to initiation of study drug. Use same imaging throughout the study. Assessment by physical exam should be done ≤ 14 days prior to initiation of study drug. If using PET-CT, use the CT portion to obtain measurements.

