9.2.2 Reporting Serious Adverse Events

All new SAEs occurring from the date the patient signs the study consent until 30 days after the last intervention or a new treatment is started, whichever comes first, will be reported. The RPCI SAE Source Form is to be completed with all available information, including a brief narrative describing the SAE and any other relevant information.

SAEs occurring after the 30 day follow up period that the investigator determines to be possibly, probably or definitely related to the study intervention should be reported.

SAEs identified as an Unanticipated Problem by the Investigator must be reported. Please refer to [Section 9.5.2](#) for details on reporting Unanticipated Problems.

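### The last scheduled adverse-event check may fall up to 7 days before the plan's own 30-day reporting period ends

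*Combined protocol and SAP*

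**What the plan says.** **Reporting period.** Section 9.1.3 covers "Routine AEs occurring between the start date of intervention until 30 days after the last intervention". The same sentence lists other end points, among them the start of a new treatment. The synopsis (Study Procedures) gives the AE period as "From time of Cycle 1 Day 1 until 30 days after receiving last dose of study drug". For serious events, Section 9.2.2 covers "All new SAEs occurring from the date the patient signs the study consent until 30 days after the last intervention", or until a new treatment starts if that is sooner.

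**Visit that closes the period.** The Table 4 column (Section 7.14) is headed "30 Day Follow- Up (± 7 days". Section 7.12 lists "Adverse events evaluation" at this visit, together with hematology and chemistry. Neither place says which date the 30 days are counted from.

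**Afterwards.** Section 7.13 says "Patients will also be followed for survival every 3 months following the 30 day follow-up visit", and adds: "Survival follow-up assessments may be collected via telephone". In Table 4 the row "Adverse Event Evaluation" is blank under Survival Follow-Up.

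**The concern.** A two-sided window suits a visit in the middle of a series, because the next visit picks up whatever an early one missed. This is the last visit in the series for AEs. If it is held early, the plan still counts the remaining days to day 30 as reporting time but schedules nobody to ask about them.

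Toxicity is a secondary objective (Section 3.2), and Sections 11.1 and 11.6 promise summaries of all adverse events. Section 1.5 also warns that diarrhea with this drug can appear late and can be dangerous, so events after the last dose are of real interest. With a maximum of 38 patients, whether a late event is found should not depend on the day the closing visit happened to be booked.

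Early visits are plausible. Tumor assessment is tied to Day 1 of a following cycle (Table 4, footnote 7), which is about 21 days after the previous dose. A patient taken off treatment at that point could have a compliant closing visit two days later, on day 23.

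**Working it through.** The plan gives no calculation to reproduce; the check is calendar arithmetic.

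**Inputs**
- End of the AE reporting period: day 30 after the last dose (synopsis; Section 9.1.3).
- Window on the last visit with an AE evaluation: 7 days either side of day 30 (Table 4).
- Later contacts: survival only, every 3 months (Section 7.13; Table 4).
- Assumption: the visit is counted from the last dose.

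**Allowed visit days**
- Earliest: 30 − 7 = day 23.
- Latest: 30 + 7 = day 37.

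**Days with no scheduled AE check** = max(0, 30 − visit day)

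| Visit day | Days not covered | Share of 30 days |
|---|---|---|
| 23 | 7 | 7/30 = 23% |
| 26 | 4 | 4/30 = 13% |
| 29 | 1 | 1/30 = 3% |
| 30 to 37 | 0 | 0% |

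**Average, for scale only.** The documents do not say when visits will actually fall. If they were spread evenly over the 15 allowed days, the mean gap would be (7 + 6 + 5 + 4 + 3 + 2 + 1)/15 = 28/15 = 1.9 days, or about 6% of the 30 days. Both this and the table measure uncovered time, not missed events.

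**Sensitivity to the anchor.** If the visit were counted from a decision to stop taken about 21 days after the last dose, the earliest compliant visit would be about 21 + 23 = day 44 after that dose and there would be no gap. The gap disappears whenever the anchor falls 7 or more days after the last dose, since 7 + 23 = 30.

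**Does another rule fill the gap?**
- Section 9.2.2: serious events stay reportable to day 30, and related ones beyond it.
- Section 7.5: AEs that led to discontinuation are followed until resolved or stable, and deaths within 30 days of the last dose are recorded. It also mentions end-of-treatment evaluations, but Table 4 has no column for them and nothing places them on or after day 30.
- Section 9.1.3: new information is reported when received, which presupposes that someone volunteers it.

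None of these schedules a check for a new non-serious AE that starts between an early visit and day 30.

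**After the fix.** With no final AE contact before day 30, the largest gap goes from 7 days to 0.

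**The case against.** The strongest reply is that reporting and visiting are different things. Section 9.1.3 defines reportable events by when they occur, so the duty continues after an early visit, and serious events, early deaths and AEs that caused discontinuation each have their own rule. That stands. It is why the point is limited to the absence of a scheduled check for new non-serious events.

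Three further limits also stand:
- A new treatment started before day 30 can end the reporting period (Section 9.1.3), which shortens or removes the gap for that patient.
- Not every late event would reach the tables. Table 7 does not mark Grade 1 or 2 events judged unrelated or unlikely for routine reporting. Section 9.1.1.3 restricts laboratory AEs to those needing active management. The synopsis records the maximum grade per event type, so for that summary a late event counts only if it is a new type or a higher grade.
- A window that opens only at day 30 could push some visits past the start of next-line therapy, where attribution is harder.

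A reader might go further and infer that 20% or so of post-treatment AEs would be lost, by assuming that risk follows SN38 exposure with its half-life of about 50 days. The documents do not support that. Section 1.3.1 reports that cumulative SN38 AUC did not predict diarrhea of Grade 2 or higher, and diarrhea is the drug's main toxicity. Nor do they support a claim that the window must always bias toxicity downward: a visit on days 31 to 37 can pick up findings from after day 30, and the plan gives no explicit cutoff rule for these at that visit.

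**Conclusion.** The inconsistency is real and small. With the visit counted from the last dose, the plan as written permits 1 to 7 days of its own 30-day AE period to pass with no scheduled check for any patient seen on days 23 to 29. The maximum is 23% of the period for one patient, and there is no gap for a visit on day 30 or later.

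What is exposed is mainly new non-serious AEs that begin after an early visit in patients who have not started another treatment. They may be undercounted; it is not shown that they would be lost. The effect on the safety tables is probably small and cannot be quantified, because the documents give neither the distribution of visit days nor a post-treatment AE rate. The primary endpoint, sample size and decision rules are untouched, and the point does not question whether 30 days is long enough. It is a cheap improvement rather than a defect that must be repaired.

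**What to change.** 1. State in Table 4 and Section 7.12 that the 30-day visit is counted from the last dose of study drug.
2. Choose one of two ways to close the period:
   - set the visit window to day 30 through day 37; or
   - keep 7 days either side, and require that any visit before day 30 be followed by a telephone AE question on or after day 30, unless new anticancer treatment has started.
3. State in Section 9.1.3 that the routine AE tables include events with onset through day 30, so that findings at a visit on days 31 to 37 are handled by rule. The separate reporting of later related serious events under Section 9.2.2 stays as it is.

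**Cost.** The first option adds no contact but reduces scheduling flexibility and may place some visits after next-line therapy has begun. The second adds one short call for patients seen early and keeps the option of an examination before new therapy; it is the better choice if early visits are expected to be common. The call would ask about AEs but would not replace a blood draw, so laboratory findings after an early visit would still rest on routine care.
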